## 1. INTRODUCTION

This statistical analysis plan (SAP) is based on the final protocol (v1.0) dated 13-Mar-2019. The plan covers statistical analysis, tabulations and listings of the study data to investigate the pharmacokinetics (PK) and safety.

The SAP is prepared by Mitsubishi Tanabe Pharma Corporation (MTPC). The statistical analysis and production of the outputs described in the SAP and QC will be conducted by

████████████████████ The final analysis and outputs will be checked by ██████████  
████████ and approved by MTPC Data Science Department.

Any statistical analysis details described in this document supersede any description of statistical analysis in the protocol.

## 2. STUDY OBJECTIVE AND ENDPOINTS

### 2.1. Study Objective(s)

To evaluate the pharmacokinetics (PK) of single doses of edaravone oral suspension in patients with Amyotrophic Lateral Sclerosis (ALS)

### 2.2. Safety Assessments

- (1) Adverse events and adverse drug reactions
- (2) 12-lead ECG
- (3) Laboratory tests
- (4) Vital signs

### 2.3. Pharmacokinetic Assessments

- (1) Drug concentration (in plasma and urine)

Unchanged edaravone, sulfate conjugate, and glucuronide conjugate

- (2) Pharmacokinetic parameters

Unchanged edaravone:  $AUC_{0-t}$ ,  $AUC_{0-24}$ ,  $AUC_{0-\infty}$ ,  $C_{max}$ ,  $t_{max}$ ,  $t_{1/2}$ ,  $Kel$ ,  $MRT$ ,  $CL/F$ ,  $V_z/F$ ,  $V_{ss}/F$ ,  $Ae$ ,  $Ae\%$ ,  $CLr$

Sulfate conjugate and glucuronide conjugate:  $AUC_{0-t}$ ,  $AUC_{0-24}$ ,  $AUC_{0-\infty}$ ,  $C_{max}$ ,  $t_{max}$ ,  $t_{1/2}$ ,  $Kel$ ,  $Ae$ ,  $Ae\%$

(t: Final concentration measurable time point)

Other PK parameters (for all PK profiles for which the  $Kel$  has been calculated):  $AUC\%_{ex}$ , Adjusted  $R^2$ , Number of  $Kel$  points, Lower limited of  $Kel$ , Upper limiter of  $Kel$

### **3. STUDY DESIGN**

#### **3.1. Phase and Type of the Study**

Phase of the study: Phase I

Type of the study: Clinical pharmacology study

#### **3.2. Study Design**

##### **3.2.1. Type and Details of Cohorts**

Single-dose, open-label

##### **3.2.2. Study Period and Evaluation Period**

**Study period:** The study period is defined as the period from the time of obtaining the informed consent to the time of completion of the end-of-study assessment or discontinuation assessment (for subjects who have entered into the follow-up period, to the time of completion or termination of the follow-up).

**Screening:** Subjects providing informed consent will be screened for eligibility to select subjects meeting all of the inclusion criteria and none of the exclusion criteria.

**Evaluation period:** The evaluation period is defined as the period from provision of informed consent to completion of the end-of-study assessment or discontinuation assessment.

**Hospitalization period:** 2 nights and 3 days (Day -1 to Day 2)

**End-of-study assessment:** The prespecified observations and tests will be performed as the end-of-study assessment, 7 days (allowance $\pm$ 2 days) after the dose of the investigational product.

### 3.3. Schedule of Study Procedures

Day (time window)	Informed consent	Screening Day -30 to -2	1																24 h Discharge	2	End-of-study  Assesment Day 8 (±2)
			-1	Admission	Pre-dose	0	5 m	15 m	30 m	45 m	1 h	1 h 30 m	2 h	4 h	6 h	8 h	10 h	12 h			
Time after dosing		Visit																	Visit		
Written informed consent	X																				
Subject characteristics		X																			
Eligibility assessment		X	X	X																	
Dosing of edaravone					X																
Height, weight, BMI a)		X	X																X		
Physical examination		X	X	X														X	X		
Vital signs		X	X	X														X	X		
12-lead ECG		X	X	X														X	X		
Laboratory tests		X	X																X		
Serological tests		X																			
Drug/alcohol abuse screening		X																			
Pregnancy test (only female)		X	X																X		
Adverse events	←																				
Concomitant medications		←																			
Blood sampling for edaravone				X	X	X	X	X	X	X	X	X	X	X	X	X	X	X			
Urine sampling for edaravone b)				←															→		

- a) Height: Only at screening; Body weight: At screening, hospitalization and end-of-study assessment (discontinuation assessment). BMI: At screening and hospitalization assessment.
- b) Urine volume will be measured for each void. A portion of the urine will be collected, dispensed into a tube containing stabilizer, and stored frozen. Urine will be forced to void at 24 hours after administration. Urine will not be collected from subjects if collection is difficult.
- c) At the time of withdrawal, the same tests will be performed as those of the end-of-study assessment.

### 3.4. Sample Size and Power Considerations

9 subjects

[Rationales for setting]

The target number of subjects was set on the assumption that it would allow obtaining results that will meet the study objectives although it is not based on statistical calculations.

## 4. PLANNED ANALYSIS

### 4.1. Final Analysis

This SAP will be finalized before database lock. Final data analysis will be conducted after database lock.

## 5. ANALYSIS POPULATIONS

PK analysis will be performed on the PK analysis set. Safety analysis will be performed on the safety analysis set (SAF). The definitions of the analysis sets are provided below. The detailed handling of subjects was determined by the sponsor, by the time of the data lock.

### (1) PK analysis set

The PK analysis set will consist of all subjects who received at least 1 dose of the investigational product and had evaluable PK data.

### (2) SAF

The SAF will consist of all subjects who received at least 1 dose of the investigational product.

## 6. STATISTICAL CONSIDERATIONS

### 6.1. Descriptive Statistics

#### (1) Non-PK related

Continuous data will be summarized descriptively using the number in the analysis set (N), the number of observations (n), mean, standard deviation (SD), median, minimum and maximum. Categorical data will be summarized using frequency counts and percentages. The denominator for the percentages will be the total number of subjects and analysis population being presented, unless otherwise specified.

#### (2) PK related

Plasma concentrations will be summarized descriptively using N, n, mean, SD, CV%, median, minimum and maximum.

The plasma and urine PK parameters will be summarized descriptively using N, n, arithmetic mean, SD, median, CV%, range (minimum, maximum), geometric mean and geometric CV%. CV% and Geometric CV% will be calculated as follows:

$$CV\% = \frac{\text{standard deviation}}{\text{arithmetic mean}} \times 100$$

$$\text{Geometric CV\%} = \sqrt{[\exp(\sigma^2) - 1]} \times 100$$

where  $\sigma$  represents the standard deviation computed on the natural logarithmic transformed concentrations.

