Attachment 1 Administrative Structure

Attachment 2 El Escorial Revised Airlie House Criteria

Attachment 3 ALSFRS-R

Confidential

List of Abbreviations

Abbreviations	Unabbreviated expressions
ALS	Amyotrophic lateral sclerosis
BCRP	Breast cancer resistance protein
BMI	Body mass index
CYP	Cytochrome P450
EDC	Electronic data capture
FSH	Follicle stimulating hormone
GCP	Good clinical practice
HBs	Hepatitis B surface
hCG	Human chorionic gonadotrophin
HCV	Hepatitis C virus
HIV	Human immunodeficiency virus
HR	Heart rate
IC ₅₀	drug concentration associated with 50% inhibition
ICH	International Council for Harmonization of Technical Requirements for Pharmaceuticals for Human Use
MedDRA	Medical Dictionary for Regulatory Activities
OAT	Organic anion transporter
PK	Pharmacokinetic(s)
QTcF	Fridericia's correction of QT interval
SAE	Serious adverse event
SOD	Superoxide dismutase
TEAE	Treatment-emergent adverse event
UGT	UDP-glucuronosyl transferase

Confidential

List of Abbreviations for Pharmacokinetic (PK) Parameters

Abbreviations	Unabbreviated expressions
Ae	Cumulative amount of drug excreted in urine
Ae%	Cumulative percentage of drug excreted in urine
AUC	Area under the plasma concentration-time curve
CL/F	Apparent total clearance
CL _r /F	Apparent renal clearance
C _{max}	Maximum plasma concentration
K _{el}	Apparent terminal elimination rate constant
MRT	Mean residence time
t _{1/2}	Terminal elimination half-life
t _{max}	Time to reach maximum plasma concentration
V _{ss} /F	Apparent distribution volume at steady state
V _z /F	Apparent distribution volume at elimination phase

Definition of Term

Term	Definition
Study period	Period from the time of obtaining the informed consent to the time of completion of the end-of-study assessment or discontinuation assessment (for subjects who have entered into the follow-up period, to the time of completion or termination of the follow-up)

Confidential

Protocol Summary

1 Study Title

Clinical Pharmacology Study of Oral Edaravone in Patients with Amyotrophic Lateral Sclerosis (ALS)

2 Study Objectives

To evaluate the pharmacokinetics (PK) of single doses of edaravone oral suspension in Patients with Amyotrophic Lateral Sclerosis (ALS)

3 Subjects

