## LIST OF PK PARAMETERS

Parameters	Definitions
AUC 0-24	Area under the plasma concentration-time curve from zero up to 24 hour
AUC 0-t	Area under the plasma concentration-time curve from zero up to the last quantifiable concentration time point
AUC 0-∞	Area under the plasma concentration-time curve from zero up to infinity with extrapolation of the terminal phase
AUC% 0ex	Area under the (plasma) concentration-time curve extrapolated from the last quantifiable concentration time point to infinity in % of the total AUC 0-∞
Ae 0-24	Cumulative urinary excretion amount of drug from zero to 24 hour
C max	Maximum plasma concentration after administration
C last	Last quantifiable concentration
CL/F	Apparent total clearance
CL r	Renal clearance
K el	Elimination rate constant from the central compartment
LLOQ	Lower limit of quantification
LOQ	Limit of quantification
MRT	Mean residence time
NC	Not calculated
t 1/2	Terminal elimination half-life in plasma concentration-time course
V ss /F	Apparent volume of distribution at steady state
V z /F	Apparent volume of distribution during terminal phase
Ae%	Urinary excretion ratio of drug

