### 7.1.3.2. Pharmacokinetic Parameters

Below the limit of quantification

For the calculation of PK parameters, actual sampling time (in hours rounded to 3 DPs) relative to dosing should be used. Concentration below the limit of quantification (BLQ) will be

imputed with a value of 0. For calculation of AUCs, missing data will be treated as if the respective sample never had been scheduled for the calculation by the linear-linear trapezoidal rule. For Ae, Ae% and CLr, geometric mean and geometric CV% will be calculated only when all the individual Ae, Ae% and CLr is greater than 0 in each sampling time point.

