MRT	h	$AUMC_{0-\infty} = \sum_{i=1}^n \frac{(t_i - t_{i-1})(t_i \times C_i + t_{i-1} \times C_{i-1})}{2} + \frac{t \times C_t}{K_{el}} + \frac{C_t}{(K_{el})^2}$ $MRT_{0-\infty} = \frac{AUMC_{0-\infty}}{AUC_{0-\infty}}$
V z /F	L	$V_z/F = CL/F \times \frac{1}{K_{el}}$
V ss /F	L	$V_{ss}/F = MRT \times CL/F$
Number of Kel points	-	will be determined using number of points used in computing Kel. If Kel cannot be estimated, zero.
Lower Limit of Kel	h	will be determined using lower limit on time to be included in the calculation of Kel
Upper Limit of Kel	h	will be determined using upper limit on time to be included in the calculation of Kel
Ae	mg	urine concentration × urine volume
Ae%	%	Ae / Dose
CLr	L/h	$CLr = \frac{Ae}{AUC_{0-\infty}}$

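### SAP 6.1(2) defines the σ in geometric CV% on log concentrations although the statistic is reported only for PK parameters, and Appendix 1 gives Ae% without the factor 100

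*SAP*

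**What the plan says.** **Geometric CV%.** SAP 6.1(2) handles two kinds of PK data separately. For the first, "Plasma concentrations will be summarized descriptively using N, n, mean, SD, CV%, median, minimum and maximum". No geometric statistic appears there. For plasma and urine PK parameters, the list ends with "range (minimum, maximum), geometric mean and geometric CV" (in percent). The formula that follows is √(exp(σ²) − 1) × 100, where σ "represents the standard deviation computed on the natural logarithmic transformed concentrations". SAP 7.1.3.2 confirms that the statistic is meant for parameters: for the urinary ones, "geometric mean and geometric CV% will be calculated only when all the individual Ae, Ae% and CLr is greater than 0".

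**Ae%.** SAP Appendix 1 gives the unit as % and the formula as Ae over dose. The protocol's list of PK abbreviations defines Ae% as "Cumulative percentage of drug excreted in urine".

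**Ae.** Appendix 1 gives "urine concentration × urine volume", in mg. The SAP's List of PK Parameters defines Ae0-24 as "Cumulative urinary excretion amount of drug from zero to 24 hour". The footnote to the schedule in SAP 3.3 says "Urine volume will be measured for each void".

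**Standing of these texts.** Protocol 10.1 leaves the detailed calculation of each parameter to the SAP. SAP Section 1 says that the SAP's statistical details override those in the protocol. Section 6.1 and Appendix 1 are therefore the controlling specification.

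**The concern.** A formula in a controlling specification should give the statistic it names when followed as printed. Two here do not. The variables that receive a geometric CV% are not the variable on which σ is defined, and the Ae% expression is a proportion labelled as a percentage.

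PK is the study's only objective. With nine patients and no hypothesis test, the descriptive tables are the result, and Ae% is a listed PK endpoint. A specification that must be overridden to obtain the right number is a weak reference for the output checks described in SAP Section 1.

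**Working it through.** The plan states no numerical result for these formulas, so there is no figure to reproduce. The check is to read each formula against the statistic it names, and then evaluate it on assumed inputs, because the documents contain no data.

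**1. Which variable receives geometric CV%?**

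| Data type (SAP 6.1(2)) | Geometric CV% reported? | σ defined on its logs? |
|---|---|---|
| Plasma concentrations | No | Yes |
| Plasma and urine PK parameters | Yes | No |

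The two columns do not match. For t1/2, CL/F or Ae there is no set of log concentrations whose SD could stand in for the SD of the log parameter.

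**2. Is the formula itself right?** Yes. √(exp(σ²) − 1) × 100 is the standard form for a log-normal variable. With σ as the SD of the log parameter:

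| σ (assumed) | Geometric CV% |
|---|---|
| 0.2 | 20.2 |
| 0.3 | 30.7 |
| 0.4 | 41.7 |
| 0.5 | 53.3 |

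Only the definition of σ needs changing. The table also shows that the result depends on which σ is used: moving from 0.4 to 0.5 raises it from 41.7 to 53.3.

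**3. Ae%.** The dose is 105 mg (Protocol 8.3).

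| Ae, mg (assumed) | As printed: Ae / 105 | With × 100 |
|---|---|---|
| 1.05 | 0.01 | 1 |
| 5.25 | 0.05 | 5 |
| 52.5 | 0.50 | 50 |
| 73.5 | 0.70 | 70 |

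CV% and geometric CV% in SAP 6.1(2), and AUC%ex in Appendix 1, all print × 100. Ae% is the exception.

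**4. Ae per collection and Ae0-24.** The SAP uses the symbol Ae in two ways.

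- *Per collection:* SAP 9.1(3) sets the digits for a pre-dose Ae and a pre-dose Ae%. SAP 8.4.2 keeps pre-dose urinary parameters out of the summaries. SAP 7.1.3.2 applies its positivity rule at each sampling time point. For one collection, concentration × volume is complete and correct.
- *Cumulative:* the List of PK Parameters defines Ae0-24 as a 0–24 h total. SAP 7.3(2) sets missing urine data to 0 when Ae is calculated, which makes sense only for a sum.

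The step from one to the other is not printed, although Appendix 1 prints explicit sums for AUC0-t and AUMC. As an illustration, take five post-dose voids with assumed amounts of 30, 20, 8.75, 4.5 and 2.5 mg. Ae0-24 = 30 + 20 + 8.75 + 4.5 + 2.5 = 65.75 mg, and Ae% = 65.75 / 105 × 100 = 62.6. CLr is written as Ae / AUC0-∞, so the text should also say which Ae it uses.

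**The case against.** The strongest reply is that nobody would program these lines literally. The geometric CV% formula sits directly under the sentence about PK parameters. The literal σ cannot be computed for CL/F or Ae, and no time point is named for it. A programmer must therefore use the parameter values, and the word concentrations is a slip. For Ae%, the unit column already says %, and 0.626 expressed in % is 62.6. Appendix 1 also leaves a conversion unprinted for CL/F: mg divided by ng·h/mL gives 10⁶ mL/h, that is 1,000 L/h, and that factor is not written out either. Finally, SAP 6.1(2) gives SD, CV%, median and range beside geometric CV%, and no test or acceptance limit depends on any of these values.

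Most of this stands, and it limits the consequence. It does not make the text right: the σ definition names the wrong variable, and Ae% departs from how the SAP writes its other percentages.

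A reader might go further than the documents allow in three ways:

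- **That the reported Ae would be the amount in a single void.** Reporting one void as the 0–24 h amount would contradict the definition of Ae0-24 and the zero rule in SAP 7.3(2). The printed product is correct for a single collection; only the summation step is missing.
- **That BLQ values set to 0 would break the logarithm.** No geometric statistic is planned for concentrations, so no such calculation arises.
- **That two independent programs would disagree.** SAP Section 1 mentions QC and checking of outputs; it does not say that there is double programming.

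**Conclusion.** The point holds as a minor specification error in two places: the definition of σ in SAP 6.1(2) and the missing × 100 for Ae% in Appendix 1. The unprinted sum for Ae0-24 is a lesser matter of clarity.

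Under literal programming, Ae% would be 100 times too small, and geometric CV% would describe a different variable by an amount that the documents do not allow anyone to state. A reader might infer that the study's tables contain these errors. The documents do not support that, because the definitions, the units and the missing-data rule together show what was meant. Sample size is unaffected, since nine was not based on a statistical calculation, and so is subject safety. The plasma PK parameter values themselves are also unaffected. Of the plasma results, only the geometric CV% is touched.

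The judgement rests on the current SAP text. Every numerical example above uses assumed inputs.

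**What to change.** Make two corrections:

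- SAP 6.1(2): σ is the standard deviation of the natural-log-transformed individual PK parameter values.
- SAP Appendix 1: Ae% = Ae / Dose × 100.

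Add one clarification in Appendix 1:

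- Keep Ae per collection = urine concentration × urine volume, which the pre-dose Ae needs.
- Add Ae0-24 = sum of Ae over all post-dose voids up to and including the 24 h forced void.
- State that the summarised Ae% and CLr use Ae0-24.

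The cost is a few lines of SAP text. Replacing the per-collection formula outright would be a mistake, because SAP 9.1(3) still reports a pre-dose Ae. If the database is already locked, Protocol 13.5 provides the route if a method is changed or added: a revised SAP and a statement in the clinical study report. In that case it is also worth confirming from the outputs that Ae% equals 100 × Ae0-24 / 105, and that geometric CV% was computed from the logs of the parameters.

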## 6.2. Data Review Meeting

Prior to database lock, a data review meeting (DRM) was conducted at November 22, 2019. Protocol deviation and handling of subjects and records, for analysis sets and evaluations, was confirmed during DRM.

No protocol deviation was observed during the study. As a results of DRM, all subject was included in SAF and PK analysis set.

The PK data handling was assessed during DRM. All PK data were considered valid and included in the calculation of PK parameters and in the summary tables and figures.

## 7. DATA CONVENTIONS

### 7.1. Analysis Variable Definitions

#### 7.1.1. Study Subjects

##### 7.1.1.1. Demographic and Other Baseline Characteristics

###### (1) BMI

BMI will be recalculated using the formula below and reported to IDP

$$\text{BMI (kg/m}^2\text{)} = \text{weight at Day-1 (kg)} / \{\text{height at screening (m)}\}^2$$

###### (2) Age at informed consent

Age (year) = year of informed consent – year of birth

Subtract 1 from the age (years) calculated above, if [Month of informed consent < Month of birth] or [Month of informed consent = Month of birth AND Day of informed consent < Day of birth].

##### 7.1.1.2. Medical History

Medical history will be coded according to the MedDRA version 22.0.

##### 7.1.1.3. Prior or Concomitant Medication

Medications will be coded according to the WHO Drug Dictionary (WHO-DD) Global B3 Format March 1, 2019.

###### (1) Prior Medication

Prior medication is any medication that was stopped prior to the investigational product administration.

###### (2) Concomitant Medication

Concomitant medication is any medication (including commercially available drugs) other than the investigational product, between the start of investigational product administration and completion of the end-of-study assessment.

## 7.1.2. Safety Assessments

### 7.1.2.1. Adverse Events

Adverse events will be coded according to the MedDRA version 22.0.

#### (1) Treatment Emergent Adverse Events/ Treatment Emergent Serious Adverse Events (TEAEs/TESAEs)

A TEAE/TESAE is classified as treatment emergent if it newly occurred after the first dose of study drug or if a pre-dose event increases in severity following the first dose of study drug.

#### (2) Adverse Drug Reaction

A TEAE is considered “adverse drug reaction” if it has been assessed as having a “reasonable possibility” in relationship to the study drug.

#### (3) Time to Adverse Events

Time to Adverse Events occurrence (days) = AE start date – date of first administration + 1

#### (4) Duration of Adverse Events

Duration of Adverse Events (days) = AE stop date – AE start date + 1

### 7.1.2.2. Laboratory Tests

Values for out of pre-defined clinically relevant will have clinically relevant values flagged set (L=Lower than normal range, H=Higher than normal range or A=Abnormal).

### 7.1.2.3. 12-Lead ECG

#### (1) Criteria for pre-defined limit

12-lead ECG:

- QTcF > 500msec
- 500 >= QTcF > 480msec
- 480 >= QTcF > 450msec
- QTcF <= 450 msec
- Change from baseline in QTcF > 30 msec
- Change from baseline in QTcF > 60 msec

## 7.1.3. Pharmacokinetics Evaluation

### 7.1.3.1. Plasma Concentration

For the calculation of the summary statistics, concentration values reported as below the limit of quantification (BLQ) will be set to 0.

### 7.1.3.2. Pharmacokinetic Parameters

Below the limit of quantification

For the calculation of PK parameters, actual sampling time (in hours rounded to 3 DPs) relative to dosing should be used. Concentration below the limit of quantification (BLQ) will be

imputed with a value of 0. For calculation of AUCs, missing data will be treated as if the respective sample never had been scheduled for the calculation by the linear-linear trapezoidal rule. For Ae, Ae% and CLr, geometric mean and geometric CV% will be calculated only when all the individual Ae, Ae% and CLr is greater than 0 in each sampling time point.

## 7.2. Analysis Visit Definitions

### (1) Non-PK related

The date of the first dose of study drug is defined as Day 1.

Unless otherwise specified, baseline will be the last observed value of the parameter of interest prior to the first intake of study drug (this includes unscheduled visits). No analysis visit window will not be performed for safety evaluation.

### (2) PK related

The allowable time window will be the following.

#### Plasma PK sampling

Nominal Time Point	Window
Predose	Within 60 min before dosing
0.083 h after dosing	Nominal time point $\pm$ 1 min
0.25, 0.5, 0.75, 1, 1.5, 2, 4, 6, 8, 10, 12 h after dosing	Nominal time point $\pm$ 5 min
24 h after dosing	Nominal time point $\pm$ 15 min

